8. RESEARCH METHODS

8.1. Study design

This study will be a retrospective database analysis utilizing data sets within the HealthVerity database (Philadelphia, Pennsylvania) covering the time period 01 December 2018 through 08 July 2021 (or latest data available) to describe the characteristics of subjects with IC conditions vaccinated with BNT162b2 and to evaluate the incidence of SARS-CoV-2 breakthrough infections.

Study period: 01 December 2018 – 08 July 2021 (or latest data available)

Index identification period: 11 December 2020 – 08 July 2021 (or latest data available; inclusive)

Index date: The first record for a SARS-CoV-2 vaccine (primary analysis: BNT162b2; sensitivity analyses: any Mrna, any authorized vaccine) from a medical claim, pharmacy claim, or chargemaster record.

Baseline period: 12-month period prior to the index vaccination date

Follow-up period: Variable period beginning after the index date and continuing until the earliest of the following: end of the study or end of continuous insurance enrollment.

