8.3. Variables

Table 1. Immunocompromising Conditions definition

Variable	Role	Data source(s)	Operational definition
Immunocompromising Conditions	Cohort Definition	HealthVerity Vaccine Data	
Subjects will be categorized into the following 12 mutually exclusive IC groups based on the algorithm detailed in Figure 1:
 
Symptomatic HIV/AIDS, solid malignancy, bone marrow transplant recipients, organ transplant recipients, rheumatologic or other inflammatory conditions, primary immunodeficiencies, other intrinsic immune conditions, chronic kidney disease or end stage renal disease, hematologic malignancy, immunosuppressive treatment only, antimetabolites only, or >1 IC condition.

PFIZER CONFIDENTIAL

Table 1. Immunocompromising Conditions definition

Variable	Role	Data source(s)	Operational definition
			
Subjects falling into more than one of these categories will be categorized as having >1 IC condition.
 
At a minimum, subjects will be required to have one inpatient claim or two outpatient claims on separate days with the IC condition of interest in the baseline period. In cases when >14 days of treatment are required it will be based on the dispensed day supply or distinct days of treatment in the baseline period.
 
The main diagnosis codes to identify IC conditions are presented in ANNEX 1. LIST OF STAND ALONE DOCUMENTS.

Table 2. Vaccination Status definitions

Variable	Role	Data source(s)	Operational definition
Any vaccination	Cohort Definition	HealthVerity Vaccine Data	
Patients with a claim for any vaccine will be considered vaccinated with any vaccine based on the following codes:
 
Pfizer/BioNTech: 91300, 0001A, 0002A, 59267100001, 59267100002, 59267100003
 
Moderna: 91301, 0011A, 0012A, 80777027310, 80777027399, 80777027315, 80777027398
 
Johnson & Johnson: 91303, 0031A, 59676058005, 59676058015
 
Source: https://www.cdc.gov/vaccines/programs/iis/COVID-19-related-codes.html

Fully Vaccinated	Cohort Definition	HealthVerity Vaccine Data	
Patients will be considered fully vaccinated if they meet any of the following definitions:
 
Two claims for Pfizer/BioNTech vaccine on separate days with >14 days of follow-up after the 2nd vaccination date. No claims for any other vaccines are allowed.

PFIZER CONFIDENTIAL

Table 2. Vaccination Status definitions

Variable	Role	Data source(s)	Operational definition

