			
 Two claims for Moderna vaccine on separate days with >14 days of follow-up after the 2nd vaccination date. No claims for any other vaccines are allowed. One claim for the Johnson & Johnson (J&J) vaccine with >14 days of follow-up after the 1st vaccination date. No claims for any other vaccines are allowed
Partially vaccinated	Cohort Definition	HealthVerity Vaccine Data	
Patients will be considered partially vaccinated if they meet any of the following criteria:
 
 One claim for Pfizer/BioNTech vaccine with > 18 days of follow-up following first vaccination date and no claims for any other vaccine. One claim for Moderna vaccine with > 25 days of follow-up following first vaccination date and no claims for any other vaccine. One claim for J&J vaccine with \leq14 days of follow-up following first vaccination date and no claims for any other vaccine.

Table 3. Patient Characteristics and Vaccine Utilization variable definitions

Variable	Role	Data source(s)	Operational definition
Age	Patient Characteristics	HealthVerity Vaccine Data	The number of years between the index date and the patient birth year. If multiple birth years are reported for the same HealthVerity ID, the maximum birthyear will be used. Age will be reported in the following categories: 16 – 17, 18 – 29, 30 – 39, 40 – 49, 50 – 64, 65 – 74, 75 – 84, and 85+. Adolescents age 12-15 will also be reported as data accumulates over monthly data cuts. Continuous statistics including mean, standard deviation (SD), median (Q1-Q3).

PFIZER CONFIDENTIAL

Table 3. Patient Characteristics and Vaccine Utilization variable definitions

Variable	Role	Data source(s)	Operational definition
			minimum, and maximum, will also be summarized.
Sex	Patient Characteristics	HealthVerity Vaccine Data	Sex will be reported as Male ('M'), Female ('F'), and Unknown

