8.9. Limitations of the research methods

There are several limitations associated with this study. The healthcare claims data are

collected for billing purposes and may be subject to misclassification, misdiagnosis, and underreporting. While the sensitivity and specificity of the Greenberg algorithm were 87.4% (95% confidence interval (CI), 80.6-92.5%) and 97.6% (95% CI, 95.0-99.9%), we cannot assess the impact that our modifications had on the accuracy of the algorithm to identify immunocompromised patients. While we used the same codes as Patel²⁵ for HIV, which included HIV only when symptomatic, we cannot be certain about the degree of immunosuppression among patients who had International Classification of Diseases (ICD) codes for symptomatic HIV/AIDS. Further research leveraging Electronic Health Records/ Lab data is warranted to increase sensitivity of capturing symptomatic HIV cases. Due to irregular capture of COVID-19 vaccinations by insurers these results may only be generalizable to a subset of insured individuals. The HealthVerity Census algorithm which links unique patients across disparate data sources may incorrectly assign the same unique identifier to different people or different identifiers to the same person, though this is expected to have negligible impact on the interpretation of results. Additionally, due to the fact that the HealthVerity Data set is comprised of multiple data sources, there may be different levels of missingness for certain variables captured in this analysis.

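### Vaccination status is set by counting claims without using the dose-specific codes, so a lone second-dose claim is dated as dose 1, classed as partial vaccination and left out of Aim 2

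*Combined protocol and SAP*

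**What the plan says.** Section 8.1 defines the anchor of the study: "Index date: The first record for a SARS-CoV-2 vaccine". Inclusion criterion 2 in section 8.2.1 equates that date with the first vaccination.

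Table 2 in section 8.3 lists the qualifying codes by product, with no dose label on any of them:

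- "Pfizer/BioNTech: 91300, 0001A, 0002A, 59267100001, 59267100002, 59267100003"
- "Moderna: 91301, 0011A, 0012A, 80777027310, 80777027399, 80777027315, 80777027398"
- "Johnson & Johnson: 91303, 0031A, 59676058005, 59676058015"

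The same table then assigns status by number of claims. Full vaccination with an mRNA product needs two claims on separate days and more than 14 days of follow-up after the second. Partial vaccination with BNT162b2 is "One claim for Pfizer/BioNTech vaccine with > 18 days of follow-up following first vaccination date and no claims for any other vaccine"; the Moderna rule is the same with a 25-day threshold. No rule refers to which administration code a claim carries.

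Table 3 reports the proportions partially and fully vaccinated in IC and non-IC patients. Table 4 and section 8.7 restrict the breakthrough definition and incidence rate (Aim 2) to the fully vaccinated. Section 8.9 says: "Due to irregular capture of COVID-19 vaccinations by insurers these results may only be generalizable to a subset of insured individuals".

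**The concern.** If vaccination claims are captured irregularly, some people who completed a two-dose series may have only one claim in the data. Where that claim is for the second dose, the code may itself show that the series was completed, but the counting rule ignores it. Three things follow.

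- The subject is dated from dose 2 as if it were dose 1. This moves the 12-month baseline window, the month of first-dose uptake, and the 14- and 28-day windows for immunosuppressant use around the first dose (Table 3). It also moves the 12-month look-back for prior infection, so an infection coded between the two doses would exclude the subject.
- With enough follow-up, the subject is reported under Aim 1 as not having completed the series.
- The subject is missing from the fully vaccinated cohort, so Aim 2 loses person-time and possibly events. Aim 2 is to be split across 12 mutually exclusive IC groups with no sample size calculation.

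The plan treats irregular capture only as a limit on generalizability. It does not recognise that it also misclassifies vaccination status.

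**Working it through.** The documents give no capture rate, completion rate or count of single-claim subjects, so there is no planned figure to reproduce. The check has two parts: apply the rules as written, then show what size would follow under stated assumptions.

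**Step 1. What the codes appear to mean.** Both two-dose products have two codes ending in A (0001A and 0002A; 0011A and 0012A). The single-dose product has one (0031A). The list therefore supports reading 0002A and 0012A as second-dose codes, but the documents do not say so. It is an assumption from here on.

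**Step 2. Apply Table 2 to a subject with one claim, carrying a second-dose code.**

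| Follow-up after the claim | Status under Table 2 | Status if the code is read as dose 2 |
|---|---|---|
| 14 days or less | neither | not yet full |
| 15–18 days (0002A) or 15–25 days (0012A) | neither | full |
| more than 18 days (0002A) or more than 25 days (0012A) | partial | full |

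The partial count is inflated only in the last row. The subject is outside the Aim 2 cohort in every row; the last two rows are where time at risk is lost.

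**Step 3. How often could this happen?** Let c be the probability that a given dose is captured, and assume capture is independent between doses. Among completers with at least one claim, the share seen only through dose 2 is

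c(1−c) / [1−(1−c)²] = (1−c) / (2−c).

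- c = 0.99: 0.01/1.01 = 1.0%
- c = 0.95: 0.05/1.05 = 4.8%
- c = 0.90: 0.10/1.10 = 9.1%
- c = 0.80: 0.20/1.20 = 16.7%

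At each c this is an upper bound on the identifiable group, because product codes (91300, 91301) and NDCs carry no dose number. If capture is instead all-or-none by person or insurer, the share is 0% whatever the average capture rate: people have both doses recorded, or neither and never enter the cohort.

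**Step 4. Effect on the reported partial share, one example.** Assume true completion q = 0.90, c = 0.95, independence, enough follow-up for every subject, and an administration code on every claim.

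- Both doses captured: 0.90 × 0.95² = 0.81225
- Dose 1 only captured: 0.90 × 0.95 × 0.05 = 0.04275
- Dose 2 only captured: 0.04275
- Truly incomplete, captured: 0.10 × 0.95 = 0.09500
- Total with any claim: 0.99275

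Partial share under Table 2: (0.04275 + 0.04275 + 0.09500)/0.99275 = 18.2%. With lone dose-2 claims no longer called partial: (0.04275 + 0.09500)/0.99275 = 13.9%. True share among those captured: 0.09500/0.99275 = 9.6%. Using the code removes about half of the excess; completers with only a dose-1 claim still look partial.

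**The case against.** Much of the opposing case stands.

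- **The meaning of 0002A and 0012A is inferred.** The list carries no dose labels and points to an outside source. The pattern is good support, but the point is conditional on it.
- **Section 8.9 does not say that single doses go missing.** A reader might infer that many two-dose recipients will have one claim. The text attributes irregular capture to insurers and speaks of a subset of insured people, which fits all-or-none capture at least as well. The 12-month enrolment requirement suggests that a dose given a few weeks before the index date would usually fall in enrolled time, so a missing first dose would reflect capture; it does not show how common that is.
- **Bias in Aim 2 is not shown.** A reader might also infer biased incidence rates or a biased IC versus non-IC contrast. That needs missing dose-1 claims to be related to infection risk or to differ by IC status, and the documents give no evidence of either.
- **Requiring two claims is a defensible, specific definition of full vaccination.** Billing data are subject to misclassification, as section 8.9 says, and a lone 0002A could be a miscoded first dose. That argues against putting these subjects into the main Aim 2 analysis.
- **The plan has generic cover.** Section 8.7 promises sensitivity analyses on key design aspects, and section 8.8 allows data sources to be excluded. Neither names this rule, so neither settles how the subjects are classified.

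What the objections do not answer is that Table 2, as written, discards dose information in codes it already lists and reports an apparent completer as a non-completer.

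**Conclusion.** The point holds as a classification gap with a known direction and an unknown size. On the assumption that 0002A and 0012A denote the second dose, every lone second-dose claim with follow-up beyond the threshold adds to the partial count, and every one with more than 14 days of follow-up is missing from the full count. How many such subjects exist cannot be derived from the documents: the share of completers with any claim runs from near 0% under all-or-none capture to at most 16.7% under independent 80% capture per dose, both assumed.

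The consequence for Aim 1 is misstatement of the partial and full proportions. For Aim 2 it is lost person-time, hence precision, which matters most in the smaller IC groups. The documents do not support a claim that the incidence rates or the IC contrast are biased. The change is worth making because it is cheap and because the count itself would show whether the problem is trivial or material.

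**What to change.** 1. In Table 2, label the administration codes by dose, after confirming their meaning against the code source the table cites. Set dose number from the code where present, before claims are counted.
2. Report subjects whose only mRNA claim is 0002A or 0012A as a separate class, *dose 2 documented, dose 1 not captured*, by IC status. Do not count them as partially vaccinated.
3. Omit this class from dose-interval statistics and from outputs dated from the first dose.
4. Keep the two-claim definition for the main Aim 2 analysis. Pre-specify a sensitivity analysis that adds this class, with time at risk starting more than 14 days after the documented second dose.
5. Add to section 8.9 that irregular capture also misclassifies vaccination status.

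The cost is a few lines of protocol text and code, using codes already in the list. There are three drawbacks. Eligibility and baseline windows for these subjects remain anchored on dose 2. Some lone 0002A or 0012A claims may be miscoded first doses. And completers with only a dose-1 claim, or only a product code or NDC, will still appear partial, so the remedy is incomplete and the report should say so.

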8.2.1. Inclusion criteria

Patients must meet all of the following inclusion criteria to be eligible for inclusion in the study:

1. Unique enrollees in the HealthVerity Vaccine dataset any time **after** 10 December 2020
2. At least 12 years on the index date (ie, first vaccination date)
3. No evidence of prior COVID-19 infection (a medical claim, pharmacy claim, or chargemaster record with an International Classification of Diseases, 10th Revision, Clinical Modification (ICD-10-CM) diagnosis code of U07.1) in the 12 months prior to the index date
4. Have 12 months of continuous enrollment with medical benefits (with or without pharmacy benefits) prior to the index date

Subjects with an IC condition were identified via an algorithm originally developed and validated by Greenberg et al²⁴ for use in administrative claims database studies. For this study, this algorithm will be modified and expanded based on expert medical opinion. The algorithm is depicted in [Figure 1](#).

Subjects will be identified as immunocompromised if they had ≥ 1 hospitalization or ≥ 2 outpatient visits on separate dates with an ICD-10-CM code on a healthcare claim indicating an IC condition or if they had usage of specific immunosuppressive medications during the 12-month baseline period. The IC case definition will incorporate 8 groups based on clinical diagnoses only, 1 group based on both clinical diagnoses and usage of immunosuppressive medication, and 2 other groups based on usage of immunosuppressive medication only, for a total of 11 groups with an IC condition ([Figure 1](#)). Subjects with >1 IC condition will also be assessed, for a total of 12 mutually exclusive groups for inclusion in this study. The list of ICD-10-CM codes used to identify IC cases by diagnosis and list of immunosuppressive medications are shown in the Annex.

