US Geographic Region	Patient Characteristics	HealthVerity Vaccine Data	
US geographic region will be derived from the patient state and categorized into the following:
 
Northeast – Connecticut, Maine, Massachusetts, New Hampshire, Rhode Island, Vermont, New Jersey, New York, Pennsylvania
 
Midwest – Indiana, Illinois, Michigan, Ohio, Wisconsin, Iowa, Kansas, Minnesota, Missouri, Nebraska, North Dakota, South Dakota
 
South – Delaware, District of Columbia, Florida, Georgia, Maryland, North Carolina, South Carolina, Virginia, West Virginia, Alabama, Kentucky, Mississippi, Tennessee, Arkansas, Louisiana, Oklahoma, Texas
 
West – Arizona, Colorado, Idaho, New Mexico, Montana, Utah, Nevada, Wyoming, Alaska, California, Hawaii, Oregon, Washington
 
Other – Puerto Rico

Payer/insurance coverage on index date	Patient characteristics	HealthVerity Vaccine Data	Payer on index date will be reported as the following categories: Commercial, Medicaid, Medicare, Unknown, or missing. If multiple payers are reported on the index date, those will be captured under an ad-hoc "Multiple" category.
Vaccine Administration Setting	Patient characteristics	HealthVerity Vaccine Data	Vaccine administration setting will be determined based on the reported place of service for the claim. Prescription claims will be assumed to have occurred in the Pharmacy setting. The most common settings will be reported.
Conditions that place or may place patients at risk of Severe COVID-19 (6 months prior)	Patient Characteristics	HealthVerity Vaccine Data	Baseline comorbid conditions that place or may place patients at risk of Severe COVID-19 infection will be assessed in the 6 months prior to index vaccination. The ICD-10-CM, ICD-10 Procedure Coding System (ICD-10-

PFIZER CONFIDENTIAL

Table 3. Patient Characteristics and Vaccine Utilization variable definitions

Variable	Role	Data source(s)	Operational definition
			PCS), Current Procedural Terminology (CPT-4), and Healthcare Common Procedure Coding System (HCPCS) codes used to identify these conditions are based on the Sentinel COVID-19 Natural History Master Protocol (https://www.sentinelinitiative.org/methods-data-tools/methods/master-protocol-development-covid-19-natural-history)

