Prevention seeking behavior (at baseline)	Patient Characteristics	HealthVerity Vaccine Data	
These variables will be assessed during the 12 month baseline period:
 
Telephone or Telehealth visits defined as a claim with any of the following procedure codes (G2012, G2010, G2061-G2063; 99205-99205, 99212-99215, 99421-99423, 99441-99443, G0425-G0427, G0406-G0408)
 
COVID-19 laboratory tests defined as a claim with any of the following CPT-4 codes (87635, 86318, 86328, 86769, 87426, 86408, 86409, 86413)
 
Flu vaccinations defined as a claim with the following procedure codes (90653-90664, 90666-90668, 90724, 90470, 90672, 90673, 90685-90688)
 
The cumulative proportion of IC and non-IC subjects receiving their first dose of COVID-19 vaccine, by month, starting from December 2020 until most recent data.

Acute Respiratory Infection Hospitalization (at baseline)	Patient Characteristics	HealthVerity Vaccine Data	Any inpatient claim that occurs in the 12 month baseline period with a diagnosis of J00-J06, J09-J18, J20-J22 will be reported
Follow-up time	Patient Characteristics	HealthVerity Vaccine Data	The number of days between the index date and the earliest of the following: end of the study or end of continuous insurance enrollment
IS drugs use	Patient Characteristics	HealthVerity Vaccine Data	The proportion of subjects with IC conditions and usage of IS drugs for >14 days during the baseline period will be reported, as well as use within 14 days and 28 days within receipt of the first vaccine dose. IS drugs exclude low-dose [<60mg/day] prednisone.

PFIZER CONFIDENTIAL

Table 3. Patient Characteristics and Vaccine Utilization variable definitions

Variable	Role	Data source(s)	Operational definition
COVID-19 supportive medication use	Patient Characteristics	HealthVerity Vaccine Data	The use of medications considered supportive for COVID-19 will be assessed in the 12-month baseline period including remdesivir, dexamethasone, doxycycline, norepihephrine, methylprednisolone, lopinavir/ritonavir, eculizumab, sarilumab, tocilizumab, losartan, azithromycin, hydroxychloroquine, siltuximab, colchicine, and convalescent plasma. Codes used to identify these treatments will be based on the Sentinel COVID-19 Natural History Master Protocol

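### Table 3 counts general visit codes as telehealth without any telehealth marker and defines flu vaccination without drug codes, so two Aim 1 descriptors would be misreported

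*Combined protocol and SAP*

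**What the plan says.** Both definitions stand in Section 8.3, Table 3, under prevention-seeking behavior, and are assessed over the 12-month baseline.

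- **Telehealth:** "Telephone or Telehealth visits defined as a claim with any of the following procedure codes (G2012, G2010, G2061-G2063; 99205-99205, 99212-99215", and from the repeated code to its end the list reads "99205-99205, 99212-99215, 99421-99423, 99441-99443, G0425-G0427, G0406-G0408". One code is enough. No place of service or modifier is mentioned, and one range has identical ends.
- **Flu vaccination:** "Flu vaccinations defined as a claim with the following procedure codes (90653-90664, 90666-90668, 90724, 90470, 90672, 90673, 90685-90688". No drug codes are listed.

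Three other places matter for comparison.

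- Table 2 identifies COVID-19 vaccine by five-character procedure codes and 11-digit codes together: "Pfizer/BioNTech: 91300, 0001A, 0002A, 59267100001, 59267100002, 59267100003". Section 8.1 takes the index vaccination "from a medical claim, pharmacy claim, or chargemaster record". For COVID-19 vaccine setting, Table 3 adds: "Prescription claims will be assumed to have occurred in the Pharmacy setting".
- Section 8.2.1 admits subjects to the diagnosis-based IC groups on one hospitalization or on two "outpatient visits on separate dates with an ICD-10-CM code on a healthcare claim indicating an IC condition", in the same 12 months. It states no visit requirement for non-IC subjects, and it does not require pharmacy benefits.
- Table 5 uses place of service to identify emergency, hospital outpatient and inpatient encounters.

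**The concern.** A row labelled telehealth should count remote visits. If 99205 and 99212-99215 also cover in-person visits, the row largely records whether the subject saw a clinician at all. The documents do not print what these codes mean. That they are general visit codes comes from the CPT code set, which the plan adopts and a coder can confirm.

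The error need not fall equally on the two cohorts. The rule that places a subject in a diagnosis-based IC group demands healthcare contact, and that contact can generate the same visit codes.

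For flu vaccine, a shot billed on a pharmacy claim that carries only a drug code would go uncounted. The same kind of record would count for COVID-19 vaccine, and the plan gives no reason for the difference.

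At stake is the accuracy of Aim 1 profile descriptors, which Section 8.7 reports for the IC, non-IC and combined groups. Section 8.7 also allows optional matching, regression or propensity scores. A covariate that partly restates IC status would serve poorly there.

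**Working it through.** The plan gives no figure for either variable, so there is nothing to reproduce. All inputs below are assumptions, chosen to show direction and range.

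**Telehealth.** Let t be the true proportion with a telehealth visit, equal in both cohorts. Let o be the probability that in-person care produces at least one listed code, independent of t.

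- Measured proportion = 1 − (1 − t)(1 − o).
- False IC minus non-IC gap = (1 − t)(o_IC − o_nonIC).

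Assumed ranges are t = 20% to 50%, o_nonIC = 60% to 85% and o_IC = 90% to 98%.

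| t | o non-IC | o IC | Measured non-IC | Measured IC | False gap |
|---|---|---|---|---|---|
| 20% | 60% | 98% | 1 − 0.80×0.40 = 68.0% | 1 − 0.80×0.02 = 98.4% | +30.4 points |
| 20% | 85% | 90% | 1 − 0.80×0.15 = 88.0% | 1 − 0.80×0.10 = 92.0% | +4.0 points |
| 50% | 60% | 98% | 1 − 0.50×0.40 = 80.0% | 1 − 0.50×0.02 = 99.0% | +19.0 points |
| 50% | 85% | 90% | 1 − 0.50×0.15 = 92.5% | 1 − 0.50×0.10 = 95.0% | +2.5 points |
| 20% | 60% | 60% | 68.0% | 68.0% | 0 |

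The last row separates the two effects. With equal in-person probabilities the gap vanishes, but a true 20% is still reported as 68%. The level is therefore overstated whenever o exceeds zero. The contrast is distorted only when o differs between cohorts. The entry rule in Section 8.2.1 makes a higher o in the diagnosis-based IC groups likely, but does not fix its size.

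**Flu vaccination.** Let c be true coverage, equal in both cohorts, and s the share of shots that leave only a drug code.

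- Measured coverage = c(1 − s).
- False IC minus non-IC gap = c(s_nonIC − s_IC).

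With c = 40% to 60%:

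- Equal s: gap 0. At s = 30%, a true 60% is measured as 0.60×0.70 = 42% in both cohorts.
- s_nonIC = 30% to 50%, s_IC = 20%: from 0.40×0.10 = +4 points to 0.60×0.30 = +18 points.
- s_nonIC = 20%, s_IC = 30%: from 0.40×(−0.10) = −4 points to 0.60×(−0.10) = −6 points.
- Equal s = 30% with a true 10-point difference: measured as 10×0.70 = 7 points, so the difference is attenuated.

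Coverage is understated whenever s exceeds zero. The documents give no pharmacy share for either cohort, so neither the sign nor the size of any false gap can be stated.

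**The case against.** The strongest reply is that these are descriptive baseline variables. No planned test, incidence rate or effect estimate uses them. The screening-method VE needs only the vaccinated proportions of the population and of cases. Section 8.7 names age and time from vaccination as example confounders and does not name these variables. All of this stands, and it limits the point to a minor one.

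A reader might go further and infer three things that the documents do not support.

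- **That nearly every subject in the diagnosis-based IC groups becomes a telehealth user by construction.** Entry is possible through one hospitalization alone, and an outpatient claim with an IC diagnosis need not carry any of the listed visit codes. Non-IC subjects have office visits too.
- **That both IC versus non-IC contrasts are artefacts.** For telehealth, an upward bias is likely but its size is unknown. For flu, equal under-capture creates no false difference, and any particular gap comes from assumed pharmacy shares.
- **That the flu rule excludes pharmacy claims.** It says "Flu vaccinations defined as a claim with the following procedure codes" and names no claim type. Only a claim without a listed procedure code is lost.

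Section 8.9 does acknowledge misclassification and underreporting in claims data. That caveat is general. It neither tells a reader that the telehealth row admits office-visit codes nor corrects the rule.

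It is also fair to say that requiring a marker trades sensitivity for specificity. That is a reason to state the choice openly, or to rename the variable.

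**Conclusion.** The point holds as a minor correction to descriptive Aim 1 variables. Followed as written, the telehealth rule overstates use. It probably also inflates the contrast for the diagnosis-based IC groups: by 2.5 to 30.4 points on the assumed inputs, and by nothing if in-person visit probabilities are equal. This rests on 99205 and 99212-99215 being general visit codes, which is a matter of the code set and not stated in the plan. The range 99205-99205 is an error on its face, and the documents do not show what was intended.

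The flu rule understates coverage to the extent that shots leave only a drug code. Its effect on the contrast is zero if that share is equal in the two cohorts and can take either sign if it is not.

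Breakthrough incidence rates and screening-method VE are unaffected. Optional exploratory models would be affected only if they used these variables.

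**What to change.** In Section 8.3, Table 3:

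1. Count 99205 and 99212-99215 as telehealth only with a telehealth place of service or modifier. Otherwise, rename the variable as outpatient or telehealth visits.
2. Replace 99205-99205 with the intended code or range.
3. Add influenza-vaccine drug codes from pharmacy claims to the flu definition, in line with the COVID-19 vaccine definition.
4. Repeat the flu result in subjects with pharmacy benefits, since Section 8.2.1 does not require them.

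This is a code-list edit plus one repeated table row, and it can enter one of the monthly data cuts that Section 8.7 foresees. There are two costs. Telehealth visits billed without a marker will be missed, and flu capture will depend partly on whether pharmacy data are available, which may itself differ between cohorts. The repeat in item 4 is there to show how much the second cost matters.
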